B9. Substudy Background. Gastric cancer is usually incurable when diagnosed at an advanced stage. About four out of five stomach cancers in the United States are diagnosed after the cancer has spread to other areas of the body, with the five-year survival rate at 4 percent¹⁰⁵⁻¹⁰⁷. Since there is no standard or routine screening test for gastric cancer in the US, it is therefore critical to develop novel biomarkers to improve prevention, risk assessment and early detection among Chinese Americans. This substudy aims to evaluate the feasibility and response rate for the collection of biosamples among Chinese Americans with a clinically confirmed diagnosis of *H. pylori*. The biosamples will be used to assess differences in oral and gut microbiome profiles before and after *H. pylori* antibiotic therapy.

C. Study Design

C1. Overall Design

The purpose of this study is to implement and test the relative effectiveness of an integrated *H. pylori* test-and-treat EHR-CHW intervention among Chinese American patients compared with usual care of EHR-only intervention. The primary outcome of interest is *H. pylori* eradication. The secondary outcomes of interest are *medication adherence, self-efficacy, health literacy and other factors*. This stomach cancer prevention study will use a 2-arm RCT design to evaluate the efficacy, adoption, and impact of an integrated EHR-based decision-support intervention with CHW-led coaching for high-risk Chinese American patients to achieve optimal adherence to *H. pylori* eradication medication regimen. An advisory group will guide the development of a user-friendly EHR intervention and culturally adapted materials relevant for Chinese Americans. The interventions will be collaboratively developed and implemented in NYC safety net hospitals and clinic sites that serve large proportions of Chinese American patients.

In Year 1, we will engage in a collaborative effort to develop and refine an evidence-based clinical decision-support and physician feedback mechanism that can be integrated into existing EHR systems. In

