During the intervention period, patients that meet the eligibility criteria will be identified. The bilingual CHWs will complete a brief screening form with potential participants in person or via phone (See *Script for Telephone Screening and Screening form*). The screening form will assess demographic characteristics, participant eligibility, interest in our program, and reasons for refusal to participate. For in-person screenings, if the patient is eligible and interested in the study, the CHW will obtain verbal informed consent for study participation and describe the randomization process (See *Combined Verbal Informed Consent*). For individuals identified from the EHR registry list, CHWs will conduct phone screenings, and will complete the verbal consent process by phone with interested, eligible individuals. CHWs will compile and share contact information for consented study participants with the study coordinator on a weekly basis. All consented participants will be randomized in a 1:1 ratio using a computer-generated randomization⁸⁷ scheme to one of the study arms.

Consented participants randomized to the EHR-CHW intervention arm will receive a standardized protocol. The protocol, designed to be flexible, consists of 4 educational sessions to be delivered in a group, or per the participant's preference one-on-one or via telephone or other social networking platforms (eg. WeChat). The sessions employ adult learning techniques and group-based learning activities. All session materials will be culturally and linguistically adapted. The in-person sessions will be held at the clinics and community spaces identified by partner agencies. Data will be collected by study staff via surveys at baseline, 2, and 6 months. Scheduled office visits will be tracked via data pulls from the EHR system. If no visit is scheduled during the follow-up period, project CHWs will conduct follow-up calls to schedule participants for data collection events in the community, at the clinic, or in their home, with permission.

C 3. Assessment of Implementation, Adoption, Sustainability, and Scalability

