To capture data on utilization patterns of the tailored EHR decision support, provider feedback tools and integrated EHR-CHW initiatives, [name] will work with MCIT to extract system files monthly that indicate date and time stamps and user logins for each time the tools were used and/or CHW embedded templates were accessed. Data will be extracted into a spreadsheet and analyzed by the study staff.

Qualitative key informant interviews (See *Key Informant Interview Guide*) will be conducted by study coordinator with key providers (1-3 at each site), administrators (1-2 at each site), and the CHWs (1 at each site). At baseline, the interviews will be incorporated into the workflow analysis to assess current satisfaction and EHR usage and health coaching. At follow-up, the interviews will assess barriers and facilitators to the implementation and adoption process of the integrated EHR-CHW intervention, intervention fidelity, and to solicit recommendations for the replication and scalability of the intervention to other clinical sites. Questions will be adapted from existing validated measures on acceptability, feasibility, adoption, organizational culture, and scalability.⁸⁸⁻⁹³

Qualitative ethnographic data will be collected through observations at the clinic sites. Ethnographic data will be collected by CHWs in Year 1 and by the study coordinator in Year 5 and will be guided by the 5 key steps in a rapid assessment process. Observations will occur in clinic waiting and administrative areas. Fidelity checklists will be conducted during CHW educational sessions and follow-up.

C4. SUBSTUDY

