The integrated EHR-CHW protocol will support team-based care by supporting feedback between clinic staff and CHWs, including: First, templates will be created that CHWs can complete and upload into the EHR. Healthcare providers will be able to access these templates using EHR and building upon existing workflow. Second, health coaching and referral materials, to be developed by the advisory committee, will be made available to providers through the EHR. Third, CHW communication with the healthcare

team will be facilitated by participation and report-backs from CHWs during regular team “huddles” or staff meetings; the frequency of participation will be site-specific and determined by findings from the workflow analysis.

Integrated EHR-CHW Protocol Intervention.

Orientation, Implementation and Training. CHWs have been trained through the NYU-CUNY Prevention Research Center Training Program in a set of core competencies, which was developed by CSAAH faculty [name] and [name].⁹⁵

Enrollment & Randomization. *H. pylori* infected individuals will be identified and recruited into the study from NYC health care facilities (NYU Langone Health – which includes NYU Langone Brooklyn, NYU Langone Brooklyn Family Health Centers and affiliated provider practices, and NYU Ambulatory Care Centers – Bellevue Hospital Center and Gouverneur Hospital). Participants will be identified by 2 approaches: 1) using ICD codes for *H. pylori* and Chinese ethnicity identified through a race and language code available in EHR, with recently diagnosed *H. pylori* infection (within 7-days) will be identified; via a EHR registry list, and 2) patients will be recruited directly from the above mentioned clinics. All consented participants will be randomized in a 1:1 ratio using a computer-generated randomization scheme⁸⁷ to one of the study arms.

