CHW Intervention Components. The intervention arm protocol consists of 4 educational sessions: session 1 will focus on medication adherence, treatment side effects, and the link between *H. pylori* and stomach cancer; and sessions 2 through 4 will focus on reinforcing session 1 themes, stomach cancer risk reduction, and links to community-based resources. The sessions employ adult learning techniques and group-based learning activities. All session materials are culturally and linguistically adapted. The in-person sessions will be held at the clinics, community spaces identified by partner agencies or by telephone. These sessions will be accompanied by phone call, text or voicemail medication and follow-up reminders in the preferred language (frequency depending on participant preference). The intervention materials will model scripts and messages informed by Social Cognitive Theory and will include reviewing and reinforcing individualized challenges, strategies and action plans for medication adherence and stomach cancer prevention.

A2. Data Collection

The recruitment and data collection protocol will be finalized with substantial feedback from the advisory group. All study staff involved in recruitment and data collection will receive a standardized training orientation on administering surveys and will be certified in human subjects research via the Collaborative Institutional Training Initiative (CITI Program).

EHR data will be used for recruitment and for the determination of primary outcomes. [name] will work with MCIT to identify potential participants from EPIC databases. During the recruitment period, registry lists will be generated weekly from EHR for physicians who have approved participation of their patients. Patients will be contacted either by phone (up to 3 calls) or in person by CHW. All preliminary EHR data will be deleted or shredded after one week of retrieval. EHR data to be shared with the study team include: demographics (gender, age, race/ethnicity (if available), language (if available), diagnosis of *H. pylori* through ICD codes, dates of clinic visits, name, and telephone number. Scheduled office visits will be tracked via quarterly EHR data pulls. EHR data will also be used to follow-up with the

outcome of treatment regimens and to determine *H.pylori* eradication via fecal stool antigen tests based on treatment follow-up procedures of physicians.

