Contact information will be collected from participants, including cell phone and home phone numbers, home and work address, email address, and Facebook/social networking account information. We will also assess whether participants are willing to receive text reminders on their cell phone. Additionally, a reminder letter and a small gift (tote bag, etc) will be sent to every participant who is willing to receive mail 4 months after enrollment. These strategies have been shown to be effective in retaining participants in community-based research.

Data will be collected by study staff via surveys at baseline, 2, and 6 months. Scheduled office visits will be tracked via quarterly data pulls from the EHR system. If no visit is scheduled during the follow-up period, project CHWs will conduct follow-up calls to schedule participants for data collection events in the community, at the clinic, or at their home, with permission. Participants will be compensated \$25 for each assessments and will receive reminder calls and/or texts 2 weeks prior to data collection events to ensure attendance.

Substudy Biosample Collection. Substudy participants will have the option of mail or in-person pick-up for receiving study materials, which include the kits to collect oral wash and/or fecal samples and return stamped envelope. Once the substudy materials are received, study staff will set up an appointment to call or meet with substudy subjects remotely via WebEx and answer any questions about sample collection and return.

Substudy subjects will have the option to provide oral wash sample only, fecal sample only, or both. Study staff who have obtained the verbal consent will document the consent on the Enrolled Participants Log. The Enrolled Participants Log is the only record linking a participant's name, subject ID and substudy ID (if applicable).

Fecal biosample collection: Substudy participants will provide fecal samples (about 8 grams which is about 2 teaspoons) in a OMNIgeneGUT fecal sample tube (*DNAgenotek, Ontario, Canada*).

Directions for performing the test:

- 1) Remove the fecal sample tube with preservation liquid inside from packaging.
- 2) Flush the toilet, allow it to refill. The stool cannot touch the toilet bowl or water. Use one of the following collection options:
 - a. Place saran wrap or provided stool collection paper over the toilet bowl to collect a sample of stool.

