B2b. Data Sources and Collection. We will use mixed methods to document challenges, barriers, and facilitators associated with implementing the multifaceted intervention; these will help to characterize feasibility and acceptability in clinic settings, to assess fidelity to the evidence-based strategy, and to determine model sustainability and scalability. Data sources will include: 1) quantitative data on utilization patterns captured from the EHR; 2) qualitative in-depth interview data (key informant interviews) from providers, clinic staff, and CHWs; and 3) ethnographic observational data of workflow at clinic sites, use of EHR tools, and organizational barriers and facilitators.

B2c. Analysis. Analysis to address this aim will be guided by the following questions:

1. Utilization Patterns: How frequently do providers utilize the integrated EHR-CHW system and does the utilization pattern change over time? Does the intervention increase the utilization and quality of measurement reports? The system utilization files from MCIT will be used to analyze utilization patterns of the enhanced decision-support or physician alert function, as well as the integrated EHR-CHW options. These data will yield descriptive trends for frequency of utilization across the clinic sites as well as an estimate of the percentage of adoption in terms of patient follow-up visits. The frequency of quality measurement reports will be described and compared 6 months pre- and post-intervention.
2. Providers and Clinic Staffs’ Attitudes Regarding the Integrated Intervention: What are providers’ attitudes regarding *H. pylori* eradication guidelines? How satisfied or dissatisfied are the providers and staff with the integrated EHR-CHW tools? What are the barriers and facilitators of point-of-care use of

the tools? How does the intervention affect providers and staffs' satisfaction with workflow for stomach cancer prevention and *H. pylori* eradication? This set of research questions and the following set will be primarily addressed with data from in-depth interviews. Qualitative analysis is described below.

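### The comparator is named but not described, the planned EHR extract would not show use of coaching materials for control patients, and the regression is worded by treatment received despite an intention-to-treat rule

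*Combined protocol and SAP*

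**What the plan says.** **Comparator.** Section C1 (Overall Design) describes the trial as the integrated EHR-CHW intervention "compared with usual care of EHR-only intervention". Section III.B1, in both the primary analysis and the power calculation, refers only to usual care.

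**Intervention arm.** Section C2 states: "Consented participants randomized to the EHR-CHW intervention arm will receive a standardized protocol". Section III.A1 gives the content as four sessions plus reminders; of these, "session 1 will focus on medication adherence, treatment side effects, and the link between" *H. pylori* and stomach cancer. Neither section has a matching description for controls.

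**EHR items.** Section III.A1 lists three supports for team-based care under the integrated protocol: templates completed by CHWs, materials for providers, and CHW report-backs at team meetings. On the second it says that "health coaching and referral materials, to be developed by the advisory committee, will be made available to providers through the EHR". No limit by arm is stated.

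**Allocation.** "All consented participants will be randomized in a 1:1 ratio using a computer-generated randomization" scheme (sections C2 and III.A1). The unit is the individual patient.

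**Logging.** Section C3 plans to "extract system files monthly that indicate date and time stamps and user logins for each time the tools were used" or the CHW templates were accessed. Section III.B2c says these data will yield "descriptive trends for frequency of utilization across the clinic sites", plus an estimate of adoption in terms of patient follow-up visits.

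**Analysis.** Section III.B1 applies intention-to-treat to all analyses and tests eradication with a chi-squared test. It then describes a logistic regression comparing patients who receive the intervention with those who do not, adjusted for confounders. Level of participation is assessed in the intervention arm only.

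**The concern.** Three gaps meet here.

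First, usual care and an EHR-only intervention are different comparators. The Background (B7b) itself argues that EHR prompts work and that EHRs can improve medication adherence. What a positive or null result means depends on which tools controls had.

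Second, with individual randomisation in shared clinics, one provider can treat patients of both arms while holding the same coaching materials. The Background (B7) names missing guidance on taking the drugs and missing side-effect information as causes of non-adherence, and session 1 covers adherence and side effects. If the materials are meant for the EHR-CHW arm only, their use for controls could raise the control rate and narrow the difference. As specified, the log could not say whether that happened.

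Third, a comparison by treatment received is not a randomised comparison. Patients who attend sessions may be those who would have completed therapy anyway. Patients lost to follow-up are counted as failures, and they are also likely to be those who received least, so this rule could exaggerate a received-versus-not contrast. Because the comparator is not described, a control whose provider used the materials has no fixed place in such an analysis.

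**Working it through.** **1. Control patients' exposure, section by section.**

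| Section | What it records | Patient or arm stated? |
|---|---|---|
| C3, monthly extract | Times and user logins when tools or templates are used | No |
| III.B2c, utilization | Trends across sites; adoption in terms of follow-up visits | Site only; no arm |
| C3, fidelity checklists | CHW sessions and follow-up | No check of controls stated |
| III.B1, participation | Level of participation | Intervention arm only |

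No row gives the share of control patients for whom a coaching item was opened.

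**2. Regression wording against the governing rule.** Within III.B1, the intention-to-treat sentence covers all analyses, while the regression sentence groups patients by receipt of the intervention. The two agree only if receipt is read as assignment, and the text does not say so.

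**3. Reproducing the stated power.** Inputs from III.B1: control 0.55, intervention 0.80, 144 patients evenly split (n = 72 per arm), two-sided 0.05. With p̄ the mean of the two rates,

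power = Φ{ [ (p₂ − p₁) − 1.96 √(2 p̄(1 − p̄)/n) ] / √( [p₁(1 − p₁) + p₂(1 − p₂)]/n ) }

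- p̄ = 0.675; 1.96 × √(2 × 0.675 × 0.325/72) = 0.153
- Denominator: √((0.2475 + 0.16)/72) = 0.0752
- (0.25 − 0.153)/0.0752 = 1.29, so power = 90.1%

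Exact enumeration of the uncorrected chi-squared test gives 90.3%. The plan's claim of more than 80% is right. For 80% power, 54 per arm (108 in all) would suffice.

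**4. What leakage would do.** Let L be the share of the 25-point gain that reaches controls on average. L is an assumption; the documents give no value. The control rate becomes 0.55 + 0.25L and the intervention rate is held at 0.80.

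| L | Control rate | Difference (points) | Power |
|---|---|---|---|
| 0 | 55.0% | 25.0 | 90.1% |
| 10% | 57.5% | 22.5 | 83.7% |
| 14.6% | 58.6% | 21.4 | 80.0% |
| 20% | 60.0% | 20.0 | 75.0% |
| 30% | 62.5% | 17.5 | 64.3% |
| 40% | 65.0% | 15.0 | 52.3% |

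By exact enumeration the 80% crossing is at L = 15.2%.

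**5. The crossing in patients.** If each exposed control gains a fraction h of the full benefit, the number exposed at the crossing is 72 × 0.1457/h:

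- h = 1: 10.5, so about 11 of 72
- h = 0.5: 21.0, so about 21 of 72 (29%)
- h = 0.25: 42.0, so about 42 of 72 (58%)

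**The case against.** **The arm is identifiable.** The opening summary splits the intervention into EHR tools and CHW navigation, and C1 says EHR-only, so a reader can infer the tools without the CHW. The consent script and key information sheet are not in the supplied text and may say more. This stands: it is too strong to infer that the arm is undefined. It is labelled, and its content is not described in the text supplied.

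**There may be no leakage to find.** A reader might infer that any use of the materials for controls is contamination, and that the EHR must therefore block it by arm. The documents do not support this. The materials sit under the EHR component, so they may belong to the EHR-only comparator; their use for controls would then be the planned comparison. Equally, they are listed as part of the integrated protocol, so restriction may be intended. The text does not settle which.

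**CHW contact with controls.** The plan says "project CHWs will conduct follow-up calls to schedule participants for data collection events". These calls have a scheduling purpose and no coaching is stated, so they are not evidence of leakage.

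**Other data would help.** Interviews, observation of tool use, and the between-arm surveys of knowledge and adherence could give hints. That is fair, but none gives exposure by patient, and gains among controls could come from ordinary counselling.

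**Intention-to-treat already governs.** It does, and the chi-squared test needs no change. The objection leaves the regression sentence in conflict with the rule.

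**The power loss is hypothetical.** This stands. Optional provider materials need not approach the benefit of four sessions with reminders, and provider reinforcement might help both arms.

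**Conclusion.** The point holds as a gap in specification and measurement, and as an internal inconsistency in III.B1. It does not show that leakage will occur or that the trial is underpowered. Power is 90% as planned and stays above 80% unless controls gain more than about 15% of the 25-point benefit: about 11 of 72 controls at full benefit, or 21 of 72 at half. These figures assume 55% and 80%, full follow-up, and an intervention rate unaffected by leakage.

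What can be said without assuming a leakage rate is that the planned extract would not reveal use for controls, and that the regression as worded is open to as-treated bias.

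A reader might also infer that a correction is needed, dividing the intention-to-treat difference by the between-arm difference in exposed share. That is not advisable, because exposure may be partial. With 20% of controls exposed at half gain, the control rate is 55 + 0.2 × 0.5 × 25 = 57.5%, the difference is 22.5 points, and 22.5/(1.00 − 0.20) = 28.1, which overstates the true 25.

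**What to change.** 1. In III.B1, state the logistic regression as a comparison of the randomised arms, and label any analysis by treatment or sessions received as exploratory. The chi-squared test stays as it is.
2. Add study ID and arm to the monthly extract in C3. In III.B2c, report by arm the share of participants in whose charts the CHW templates or the coaching and referral materials were opened.
3. While making these edits, state in C2 and III.A1 which EHR tools controls receive, and whether the coaching materials are part of the EHR-only comparator. If they are, item 2 measures delivery of the comparator; if not, it measures leakage.

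An arm flag that restricts access in the EHR is optional. It would have to work across several facilities, including two hospitals where III.A1 says Epic is still being implemented, and the documents give no basis for costing it.

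The cost is two more fields in an existing extract and a few sentences of text, with no extra patients. The limits are that an opened item is not proof of coaching, and spoken advice is not captured.
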